- Individuals who agree to participate in this study will be enrolled during an initial screening visit which they will have independently sought and scheduled. Their participation will involve one procedure visit, two brief follow-up visits, and three online completion of surveys. We anticipate that it will take approximately 15 months from date of enrollment to complete each individual subject’s procedure and follow-up visits, allowing time for flexibility in scheduling based on the clinician and subject’s schedules.
- We estimate that it should take approximately three months to enroll 75 subjects. We anticipate this being feasible based on the four participating clinicians’ current schedules. Roughly, an orthopaedic surgeon may see upwards of 50 patients a day. Approximately 10% of these patients have knee OA and potentially qualify for the study.

PROTOCOL TITLE: “Evaluating the efficacy of micro-fragmented adipose tissue and intra-articular corticosteroid injections for symptomatic knee osteoarthritis: a randomized, placebo controlled study”

- *We anticipate the data analysis to take a maximum of two months following the completion of all data collection.*

7. Study Endpoints

- 7.1. *This study will conclude once all active, enrolled participants have completed their one-year follow-up.*
- 7.2. *Participants will be followed via standard of care and monitored at follow-up appointments. After we have had 10 participants enrolled in each group, we will do a preliminary evaluation of the available data.*
- 7.3. *Not applicable. We will not have exploratory endings.*

8. Research Setting

- 8.1. *Research will be conducted at the University of New Mexico Hospital Orthopaedic Clinics of [name], [name], [name] and [name], PA-C. Research, including all patient visits and procedures, will also be conducted at the CTSC.*
- 8.2. *Participants will be recruited from the patient population at the clinics of [name], [name], [name] and [name], PA-C at the University of New Mexico’s Orthopaedic Department. Since all potential participants will be independently seeking care for osteoarthritis, the participating clinicians and research staff will screen the patients for inclusion criteria during their standard examination.*
- 8.3. *Procedures and follow-up visits will be performed at the CTSC facilities on North Campus.*
- 8.4. *Not applicable. There will be no community advisory board*

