- 13.2. *Since patient perception of post-treatment pain as measured by the VAS scale is a main variable of interest in our hypothesis, we searched the literature for previous studies in which the variability of pain using a VAS scale was investigated.²⁰⁻²³ We estimated that the standard deviation likely to be found for our own observations will be approximately 35 on a 100 point scale, conservatively. We assume that most clinicians will consider a difference in post-treatment pain of about 15 points to be clinically important, as supported by Tashjian et al, who estimated 1.4 cm as the minimal clinically important difference on a 10 cm scale. To determine an adequate sample size for our pilot, we assumed average change in pain score over the follow-up to be 10-15, and standard deviation to be 10-20. To have 80% power with a 5% Type I error an approximate 2-way ANOVA model suggest sample size in the range of 18-49 per group. We adopt n=22 as our minimum sample size per group based on the assumption of 15-point change in pain score over time on average and a 20-point standard deviation over time.*

14. Provisions to Monitor the Data to Ensure the Safety of Subjects

- 14.1. *Corticosteroids are standard of care. Lipogems® is approved for use in orthopaedics and arthroscopic procedures. Participants will be closely followed by the participating clinicians/investigators through the follow-up visits required for participation. All measures will be taken to ensure that participants receive appropriate care.*
- 14.2. *Patients will be informed of the risks of participating prior to enrolling in the study and may choose to enroll or not enroll. They will be reminded of expected post-procedural findings and will be monitored for adverse reactions by the participating clinicians at their follow-up visits.*
- 14.3. *The data monitoring committee will consist of [name], [name] [Orthopaedic Sports Medicine], [name] [Orthopaedic*

PROTOCOL TITLE: “Evaluating the efficacy of micro-fragmented adipose tissue and intra-articular corticosteroid injections for symptomatic knee osteoarthritis: a randomized, placebo controlled study”

Sports Medicine]; this committee will conduct a preliminary review of the existing data once 10 participants have been enrolled in each group.

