- 14.4. *The existing literature has been reviewed regarding Lipogems®. A board certified plastic surgeon was consulted regarding adverse effects of lipoaspiration procedures and the adverse risks are detailed in this protocol and the consent form.*
- 14.5. *N/A. Safety data is not collected in this study.*
- 14.6. *The research will be suspended and/or terminated if there is an unexpected serious adverse event that requires further investigation.*

15. Withdrawal of Subjects

- 15.1. *We do not anticipate any medical reasons to withdraw subjects from the study without their consent. If participants are not adherent and miss follow-up appointments, refuse to be scheduled, or do not respond to scheduling requests, they will be withdrawn from the study.*
- 15.2. *Participants may withdraw at their request and continue to seek standard of care treatments with the physician of their choice. No labs/tapering of meds/or physical exams are necessary to withdraw.*
- 15.3. *Partial withdrawal will be permitted if a patient desires to continue participating in data collection but no longer wishes to be seen for follow-up. The questionnaires would be completed online only. All previously collected data will still be used for research purposes unless the patient explicitly asks for data to be excluded.*
- 15.4. *If a patient withdraws, all previously collected data will still be used for statistical analysis unless the participant explicitly asks for their previous data to be excluded from further consideration. Describe the disposition of existing data/specimens when a subject withdraws.*
- 15.5. *If a patient requests to be withdrawn, [name], the principal investigator, must be made aware. If the patient requested that their data be destroyed and not used for analysis, then the data will be properly destroyed. Otherwise, data that was collected prior to withdrawal from the study may be used for analysis.*

16. Data Management/Confidentiality

- 16.1. *Members of the research team will be permitted to access the participants' medical records through PowerChart to confirm participant eligibility and document procedures and follow-up visits. PHI will be reviewed as part of the normal screening process in clinic.*
- 16.2. *Members of the research team will have access to direct identifiers only as necessary to confirm participant eligibility and document procedures and follow-up visits.*

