Lipogems® Injection 7cc of autologous adipose tissue	1 (randomization dependent)		
Lipoaspiration 25-30cc of adipose tissue harvested	1 (randomization dependent)		
Intra-articular corticosteroid injection 2cc (80mg) of Kenalog®-40 (triamcinolone acetonide injectable suspension, USP) plus 5 cc 1% lidocaine	1 (randomization dependent)		
Placebo saline injection 7cc sterile saline	1 (randomization dependent)		
Procedure Visit	1		
Follow-Up Visits (6 weeks, 6 months)	2		
Standard of Care Procedures	Number of Samples/Procedures	Responsible Party	
		Study	3 rd Party Payer or Participant
Evaluation by clinician prior to participation	1		
Routine x-rays prior to participation	Varies by clinician		
_____	_____		

22.2. *There are no additional costs to participants.*

22.3. *The study will pay for all procedures and drugs involved in the study, including: corticosteroids and Lipogems®. Lipogems® has agreed to cover the costs of the kits for all study participants randomized to receive Lipogems®.*

22.4. *While we do not anticipate any serious adverse events, there are risks involved with undergoing medical procedures. Corticosteroid injections are currently included as part of the standard of care for treating osteoarthritis of the knee, and Lipogems® is FDA approved for autologous use in orthopaedic surgery. Thus, any adverse events experienced by the patient will fall under insurance coverage for standard of care procedures. All adverse events will be reported as required by the University. Depending on the severity of event, the investigators will consider the adverse event and reserve the right to hold enrollment or close the study early.*

22.5. *See consent form for discussion of costs.*

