PROTOCOL TITLE: “Evaluating the efficacy of micro-fragmented adipose tissue and intra-articular corticosteroid injections for symptomatic knee osteoarthritis: a randomized, placebo controlled study”

23. Compensation

23.1. Participants will be compensated for their participation by receiving a reloadable gift card. They will receive \$25 at each in person follow-up visit. They will be compensated \$10 each time they complete the online surveys. Each participant will be asked to return for 2 follow-up visits (6 weeks and 6 months, post-procedure) and complete the online surveys 3 times for a total of \$80 compensation for participating.

24. Compensation for Research-Related Injury

24.1. If a patient elects to withdraw from the study, i.e. for further treatment/care elsewhere, the patient may withdraw. We do not anticipate any more risk than standard of care would provide to the patient. The patient can elect to pursue standard of care treatments as determined by the patient and their physician.

24.2. Study subjects will be monitored at follow-up appointments. If a subject is unhappy with their treatment outcome throughout the course of the study, they may elect to withdraw from the study and pursue their own care with the physician of their choice.

25. Consent Process

25.1. Participants must provide research staff with informed consent prior to enrolling in the study.

25.1.1. Consent may be obtained by [name], [name], [name], [name], and [name] and any other approved investigators listed in the Click IRB record. The process for obtaining informed consent and consent form will be reviewed with each member of the research staff responsible for obtaining consent by [name].

25.1.2. Consent will take place at the various clinics/hospitals associated with the University of New Mexico Hospital and the Orthopedics Department. Consent will only be obtained in a private patient room. No one besides the patient and study staff will be in the room at the time of consent. If the patient requests a family member or friend be in the room during the time of their appointment/consent, the patient’s request will be honored.

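### Section 14.5 says no safety data are collected, which is inconsistent with 14.2, 14.6 and 22.4; visit monitoring is promised, but no adverse-event item is listed at the five post-injection contacts

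*Combined protocol and SAP*

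**What the plan says.** All references are to the combined protocol and SAP.

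- **14.5** answers its item with "N/A. Safety data is not collected in this study".
- **14.6**, the next item, says: "The research will be suspended and/or terminated if there is an unexpected serious adverse event that requires further investigation".
- **22.4** says: "All adverse events will be reported as required by the University". It continues: "Depending on the severity of event, the investigators will consider the adverse event and reserve the right to hold enrollment", or to close the study early. Reporting is mandatory here; a hold or closure is at the investigators' discretion.
- **14.2** says participants will be "monitored for adverse reactions by the participating clinicians at their follow-up visits". Sections 14.1, 7.2 and 24.2 speak in similar general terms, for example "Participants will be followed via standard of care and monitored at follow-up appointments".
- **3.1** limits the study to effectiveness and sets safety aside as a question.
- **12.1, items 3 and 5**, list WOMAC, VAS, KOOS and a medication log at 2 weeks, 6 weeks, 3 months, 6 months and 1 year. The 6-week and 6-month contacts are in person with a research staff member; the other three are online, or by phone where there is no internet access.
- **14.3** has a committee look at whatever data exist once 10 participants per group are enrolled. It does not say whether those data include adverse events.

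**The concern.** A suspension rule and a reporting duty work only if the study learns of events and can judge how serious they are. The section on monitoring participants' safety says no such data are collected, and the list of study procedures contains no question, form or record for them. Staff who follow 14.5 as written would leave 14.6 and 22.4 without a defined input. Whether an event is noticed could then depend on who happens to mention it and when.

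This matters most for the Lipogems arm, which adds an abdominal fat harvest. Section 18.1 lists risks specific to that step, including fluid or blood collections that need draining, infection and, very rarely, skin necrosis. Section 18.2 accepts that unforeseen risks are possible. The other two arms have no harvest site, so informal noticing need not work equally across arms.

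**Working it through.** The check is mainly a comparison of sections, with a few counts.

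**1. Number of contacts.** Item 3 of 12.1 gives 2 weeks, 6 weeks, 3 months, 6 months and 1 year, which is 5. Section 6.1 gives 2 visits + 3 online surveys = 5. The payment in 23.1 agrees: 2 x $25 + 3 x $10 = $80, as stated there.

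**2. Adverse-event items.** The four named instruments at each contact are WOMAC, VAS, KOOS and the medication log. Contacts with an adverse-event item listed: 0 of 5. This counts named instruments. The VAS does record knee pain at every contact, and 18.1 names pain as a local reaction, so that symptom is captured in the same way in all arms. Nothing listed is directed at the harvest site or at other events between visits.

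**3. Reach of the monitoring in 14.2.** It is tied to follow-up visits. Sections 6.1, 12.1, 22.1 and 23.1 give two (6 weeks and 6 months), so it reaches 2 of 5 contacts. Section 25.1.15 refers to four follow-up examinations by clinicians, without dates; if those fall on scheduled contacts, the reach is 4 of 5. Neither figure covers all five.

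**4. Who is present.** Item 5 of 12.1 places the two visits with a research staff member. Section 14.2 names clinicians, 9.2 makes clinicians responsible for medical decisions at follow-up visits, and 27.1 speaks of physical findings conveyed in person. Clinician involvement is implied, but the sections do not agree on the role.

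**5. Gaps on the two-visit schedule.** Before week 6 the only scheduled contact is the week-2 survey. After the 6-month visit, 52 - 26 = 26 of 52 follow-up weeks remain, with no further visit. Partial withdrawal under 15.3 (online questionnaires only) removes any visits still to come.

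**6. Withdrawal.** Section 24.1 allows participants to leave for care elsewhere, 15.2 requires no examination, and 15.5 requires that the principal investigator be told of the request. No section requires the reason, or any event behind it, to be recorded.

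**7. Timing of the committee review.** It is triggered by enrollment of 10 x 3 = 30 participants. Section 6.1 expects 75 in about three months, taken here as 13 weeks. Assuming even accrual and balanced allocation, 30 are reached at 30/75 x 13 = 5.2 weeks, before any 6-week visit is due. Slower accrual would relax this.

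**8. Cost and precision of a remedy.** Forms: 75 x 5 = 375. With zero events among n participants, the one-sided 95% upper limit for the true rate is 1 - 0.05^(1/n):

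- n = 22 (stated minimum per arm): 0.127
- n = 25 (target per arm): 0.113

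**The case against.** The strongest reply is that 14.5 is a not-applicable answer on a form and, read with 3.1, means only that there is no safety research dataset. Clinical monitoring under 14.2, suspension for a single unexpected serious event under 14.6 and University reporting under 22.4 can all run without one. That reading is plausible, and it explains why there is no safety endpoint. But 14.5 does not say it, and it still leaves open how events reach the people who must act.

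Other information channels exist: 16.3 gives the team access to the medical record where study visits are documented, the medication log may hint at an event, and 15.5 alerts the principal investigator to withdrawals. These are indirect. The sections do not say that care obtained elsewhere is captured, and a log entry identifies neither the event nor its seriousness. University requirements and the consent form, to which 22.4 and 14.4 refer, may tell participants how to report problems; neither is in the text reviewed, so the gap is established only for the visible plan.

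A reader might infer three stronger things that the documents do not support:

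- That nobody watches for harm. Sections 14.1, 14.2, 7.2, 9.2, 24.2 and 27.1 promise or imply monitoring at visits.
- That 22.4 obliges the investigators to hold enrollment or close the study. It reserves the right to do so; only 14.6 is mandatory.
- That monitoring certainly reaches just two contacts. Section 25.1.15 gives a different number.

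**Conclusion.** The inconsistency is real: 14.5 as written cannot stand beside 14.2, 14.6 and 22.4. The procedures do not resolve it, since 0 of 5 post-injection contacts lists an adverse-event item, and visit monitoring reaches two contacts on most sections' count or up to four on that of 25.1.15. Uncaptured events are chiefly those at the harvest site or elsewhere that arise between visits or lead to withdrawal.

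This should be fixed, but it is not a fatal flaw. The efficacy estimate is unaffected, monitoring at visits is promised, and a benign reading of 14.5 is available. The conclusion rests on the instruments as named in 12.1 and assumes that their contents include no added adverse-event question. The committee-timing point also depends on the accrual forecast in 6.1 and is secondary.

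**What to change.** - Reword 14.5 to state what is meant, for example that there is no safety endpoint but adverse events are recorded.
- Reconcile it with 14.2, 14.3, 14.6, 22.4, 12.1 and 25.1.15, including the number of follow-up visits and the role that conducts them.
- Add a short standard question set (knee, harvest site where there is one, care sought, serious yes/no) to the existing survey and visit forms at all five contacts in all three arms, and ask it once at withdrawal.
- Name the role that reads the replies.
- Include descriptive by-arm counts in the 14.3 review.

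The cost is protocol wording, a few items on existing forms and one descriptive table, with no added visits. Existing staff would have to read about 375 short forms for 75 participants, plus any completed at withdrawal. The counts should be presented as descriptive only: at 22 to 25 per arm, an arm with no events remains compatible with a true rate of about 11% to 13%, so the table cannot show that a treatment is safe.

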Intra-articular knee injections, such as corticosteroids and Lipogems®, are employed in routine clinical practice for the treatment of knee osteoarthritis. With any injection, there is a risk of local adverse reaction such as pain or swelling, and a risk of infection. In addition to an injection, Lipogems® requires a lipoaspiration procedure from the patient's abdomen. Some risks of lipoaspiration include seromas and hematomas requiring drainage, infections, changes to the skin including hyperpigmentation, scarring, or induration. Very rarely, more serious complications (including skin necrosis or local anesthetic toxicity) may arise.^{24,25}

18.2. *We have received input from a board certified plastic surgeon on the risks of lipoaspiration. We have also reviewed the existing literature. Corticosteroid injection is part of the standard of care for treating knee osteoarthritis. As Lipogems® is still a relatively new treatment option, there may be unforeseen risks.*

18.3. *Patients who are pregnant will not be eligible for participation. Patients must verbally confirm they are not pregnant prior to enrollment in the study and prior to receiving their injection.*

18.4. *Not applicable. There are no risks to others who are not subjects.*

PROTOCOL TITLE: "Evaluating the efficacy of micro-fragmented adipose tissue and intra-articular corticosteroid injections for symptomatic knee osteoarthritis: a randomized, placebo controlled study"

18.5. To minimize risk, all injections will be performed following standard of care sterile techniques and treatment guidelines. We will have a board certified plastic surgeon trained in lipoaspiration train the study investigators accordingly. To protect patient confidentiality, we will take the necessary precautions to protect patient data. All electronic files will be password protected and stored on a password protected computer behind a locked door. All paper documents will be kept in a locked filing cabinet in a locked office.

19. Potential Benefits to Subjects

19.1. Potential benefits include the possibility of reduced pain and/or increased functionality of the affected knee after injection with Lipogems® or corticosteroids.

20. Recruitment Methods

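### Section 14.5 says no safety data is collected, although 14.2 and 22.4 provide for adverse events, and no text takes those events by arm to the section 14.3 committee

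*Combined protocol and SAP*

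**What the plan says.** The relevant text is spread over sections 14, 18 and 22 of the combined protocol and SAP.

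- **14.2**: participants "will be monitored for adverse reactions by the participating clinicians at their follow-up visits".
- **14.3**: a data monitoring committee is named, and "this committee will conduct a preliminary review of the existing data once 10 participants have been enrolled in each group". No other review is described.
- **14.5**: the item is marked not applicable, followed by "Safety data is not collected in this study".
- The mandatory suspension rule stands in **14.6** and reads: "The research will be suspended and/or terminated if there is an unexpected serious adverse event that requires further investigation".
- **18.1**: "Some risks of lipoaspiration include seromas and hematomas requiring drainage, infections, changes to the skin including hyperpigmentation, scarring, or induration". It then adds: "Very rarely, more serious complications (including skin necrosis or local anesthetic toxicity) may arise".
- **22.4**, under Economic Burden to Subjects: "All adverse events will be reported as required by the University". It continues: "Depending on the severity of event, the investigators will consider the adverse event and reserve the right to hold enrollment or close the study early". The same item opens by saying that no serious adverse events are anticipated.

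Section 3.1 says that the trial evaluates effectiveness and not safety.

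**The concern.** Taken literally, 14.5 cannot stand beside 14.2 and 22.4: events that are watched for and reported must be recorded somewhere. The practical question is who sees them. The protocol places a monitoring committee in its section on participant safety, but its only stated review is not promised any adverse-event data, and nothing sends it a serious event that occurs afterwards.

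This matters mainly for the Lipogems arm. Those participants alone undergo lipoaspiration, the protocol has no preliminary data (2.2), and it accepts that there may be unforeseen risks (18.2). A pattern of harm confined to one arm is what a by-arm look by a committee is meant to catch.

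**Working it through.** The documents give no adverse-event rate and no safety calculation, so there is no figure to reproduce. The check is mainly of the text.

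**Step 1. Will event information exist?** Yes. It arises from monitoring (14.2) and reporting (22.4). Under 16.3, procedures and follow-up visits are also documented in medical records that the research team can access.

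**Step 2. Is it study data?** No sentence says so. Section 12.1 lists the WOMAC, VAS, KOOS and a medication log, at baseline and at 2 weeks, 6 weeks, 3 months, 6 months and 1 year. It lists no adverse-event form.

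**Step 3. Does the committee receive it at its review?** Section 14.3 does not say what the data under review contain, and does not mention adverse events or presentation by arm.

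**Step 4. Does the committee receive later serious events?** Section 14.6 mandates suspension or termination only for a serious event that is unexpected and needs further investigation. It names neither the committee nor any decision-maker. Section 22.4 names the University and the investigators, not the committee. *Serious* is not defined, so the status of a drained seroma or hematoma is open.

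**Illustrative arithmetic.** Inputs from the documents: 75 enrolled in about three months, taken as 13 weeks (6.1); 25 per arm planned, 22 minimum (5.3); review at 10 per group (14.3); first in-person visit 6 weeks after injection (12.1). Assumptions: even enrolment, injection on the day of enrolment, and all event rates.

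*Share of the Lipogems arm enrolled after the review*, if that arm stands at exactly 10:
- (25 − 10)/25 = 60%
- (22 − 10)/22 = 55%

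*Number past the 6-week visit when the review is triggered* = number enrolled − 6 × weekly rate (zero if negative):

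| Case | Weekly rate | Calculation | Past 6 weeks |
|---|---|---|---|
| 30 enrolled, 13-week pace | 75/13 = 5.77 | 30 − 34.6 | 0 |
| 38 enrolled, 13-week pace | 5.77 | 38 − 34.6 | about 3 |
| 30 enrolled, 26-week pace | 75/26 = 2.88 | 30 − 17.3 | about 12 to 13 |
| 30 enrolled, 52-week pace | 75/52 = 1.44 | 30 − 8.7 | about 21 |

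The 38 is the simulated mean number needed to reach 10 per group under simple 1:1:1 allocation. Section 3.3 stratifies for balance, so the number needed is probably lower. At 30 enrolled, anyone is past 6 weeks only if full enrolment takes longer than 6 × 75/30 = 15 weeks.

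*Chance of at least one event* = 1 − (1 − p)^n:

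| Assumed p | n = 25 | n = 15 (enrolled after review) |
|---|---|---|
| 0.1% | 2.5% | 1.5% |
| 0.5% | 11.8% | 7.2% |
| 1% | 22.2% | 14.0% |

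*What a tally could show.* With complete capture, zero events in n participants gives a one-sided 95% upper bound of 1 − 0.05^(1/n): 25.9% for n = 10 and 11.3% for n = 25. A by-arm tally in this trial supports case-by-case judgement; it cannot establish that a harm is rare.

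**The case against.** The strongest reply is that 14.5 has been read too literally. It is marked not applicable, the form's question is not shown, and 3.1 disclaims safety as an aim. The natural meaning may be that there is no safety endpoint. That reading is plausible and accepted here. It settles what 14.5 was meant to say, but not where the reported events go.

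A reader might infer three stronger things, none of which the documents support.

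- *That a serious harm listed in 18.1 escapes the suspension rule and never reaches the committee.* Nothing says that a listed harm is therefore expected. Section 22.4 anticipates no serious events and 18.1 calls these harms very rare, so 14.6 may well cover skin necrosis or local anesthetic toxicity. The text is unclear rather than exclusionary. On either reading 14.6 leaves the committee out.
- *That harms would go unreported or unmanaged.* Section 22.4 is a genuine route: events are reported, and the investigators can hold or close the study. University rules not shown may add oversight. Committee names are removed, so a member who is also an investigator may already see the reports. None of these steps is required by the protocol.
- *That the committee's review is blind because few or no participants have reached 6 weeks.* Clinicians perform the procedures themselves, so harm at the procedure would be seen that day. The data under review could also include reports made under 22.4. The timing table shows only how little scheduled in-person follow-up might exist by then.

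It is also fair that this is a 75-person, single-site, single-injection trial of marketed products.

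**Conclusion.** The point holds in limited form. The wording of 14.5 conflicts with 14.2 and 22.4, and the protocol does not require adverse events to reach its own committee, whether by arm at the stated review or individually if serious and later. What remains is discretionary handling by the investigators and University reporting.

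Severity is minor to moderate. This is a cheap improvement to participant safety, and no efficacy estimate, test or sample size is affected. The conclusion rests on the text alone. The event probabilities rest on assumed rates and indicate how often a referral route might be used, not how often an event would be mishandled.

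**What to change.** Amend three items and add one definition.

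- **14.5**, replace the sentence with: *Safety is not a study endpoint. Adverse events found under 14.2 or reported under 22.4 are tallied by arm, with serious events identified, and given to the section 14.3 committee.*
- **14.3**, add that the 10-per-group review includes this tally.
- **14.6**, keep the suspension rule and add: *Every serious adverse event, whether or not listed in 18.1, is referred to the section 14.3 committee, which records a decision to continue, pause or stop.*
- **Definition of serious**: death, threat to life, hospital admission, lasting harm or an unplanned operation, plus skin necrosis and local anesthetic toxicity by name. A seroma or hematoma drained in clinic is tallied but not referred.

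The cost is a running tally, drawn from information that 14.2 and 22.4 already generate, and an occasional extra committee review or short enrolment delay, sometimes for an unrelated event. Each 1% of the 75 participants with a serious event adds 0.01 × 75 = 0.75 referrals on average. No visit, endpoint or automatic pause is added. The tally would be only as complete as the monitoring and reporting that feed it.
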